**Title: A Multi-center, Randomized, Open-label, Controlled Trial to Evaluate the Efficacy and Tolerability of Hydroxychloroquine (HCQ) in Adult Patients with Mild to Moderate Coronavirus Disease (COVID-19) Compared to Standard of Care Treatment**

## **1. INTRODUCTION**

### **1.1 BACKGROUND AND RATIONALE:**

On December 31, 2019, an outbreak of respiratory illness later proved to be caused by a novel coronavirus, officially named Coronavirus Disease 2019 (COVID-19), was notified first in Wuhan, a city of Hubei province, People's Republic of China (PRC). COVID-19 rapidly spreads in China and to other parts of the world. Currently more than 370,000 laboratory-confirmed cases have been reported worldwide, and the case count has been rising daily, and caused a global health emergency. As of March 29, 2020, there were 298 confirmed cases in Taiwan.

The effective medical treatment against COVID-19 infection is still unknown. Chloroquine phosphate is a well-known antimalarial drug which has been on the market for many years. Recently, *in vitro* study shown that Chloroquine is effective at both entry and at post-entry stages of the COVID-19 infection of Vero E6 cells with promising results. Chloroquine is also an immune-modifier and could distribute to the whole body including lung. Also, chloroquine is cheap and safe, and could be a promising agent against COVID-19 infection. However, only hydroxychloroquine (HCQ) with the extra hydroxyl group is available in Taiwan. Therefore, hydroxychloroquine instead become the best choice for the treatment candidate, since it shows higher *in vitro* potency (EC50) against COVID-19 with lower toxicity while retaining the original effect which compared with chloroquine.

### **1.2 STUDY OBJECTIVES**

#### **1.2.1 Primary Objective:**

- To evaluate the efficacy of HCQ, with respect to the time to negatively RT-PCR assessments in COVID-19 patients.

#### **1.2.2 Secondary Objective:**

- To evaluate the efficacy of HCQ in the aspect of virologic assessments in COVID-19 patients (e.g. viral load and clearance)
- To explore the efficacy of HCQ regarding the change of clinical symptoms in COVID-19 patients (e.g. TTCR; proportion of discharge, CNS and respiratory symptoms; mortality)
- To evaluate the safety and tolerability of HCQ in COVID-19 patients

## **2 ELIGIBILITY ASSESSMENT AND ENROLLMENT**

### **2.1 ELIGIBILITY CRITERIA**

#### **2.1.1 Inclusion Criteria**

1. Male and female age between 20-79 years
2. Patients who had fever (central temperature  $\geq 38^{\circ}\text{C}$ ) or acute upper respiratory symptoms and laboratory confirmation (rRT-PCR) for COVID-19, with available same type of upper respiratory tract specimens from screening evaluation to the initial testing within 4 days of initial testing
3. Patients have mild (no pneumonia) to moderate disease (pneumonia without respiratory distress) according to the following World Health Organization (WHO) definition of COVID-19 clinical syndromes:

- Mild (Mild illness):

Patients with uncomplicated upper respiratory tract viral infection, may have non-specific symptoms such as fever, fatigue, cough (with or without sputum production), anorexia, malaise, muscle pain, sore throat, dyspnea, nasal congestion, or headache. Rarely, patients may also present with diarrhoea, nausea and vomiting.

- Moderate (Pneumonia):

Adult with pneumonia but no signs of severe pneumonia and no need for supplemental oxygen.

4. Willing and able to comply with the study procedure and sign a written informed consent

#### 2.1.2 Exclusion Criteria

1. Patients with the medical history of hypersensitivity to chloroquine, chloroquinine, or hydroxychloroquine
2. Patients with retinal disease, hearing loss, severe neurological and mental illness
3. Patients with pancreatitis
4. Patients with severe lung, liver (alanine aminotransferase (ALT)/aspartate aminotransferase (AST) elevation more than 3 times the normal upper limit), kidney (estimated glomerular filtration rate [eGFR] <30 mL/min/1.73m^2, using the MDRD or CKD-EPI methods), brain, haematological diseases or other important systemic diseases
5. Medical history of uncontrolled but clinically significant abnormal cardiac conduction abnormalities at electrocardiogram (ECG) at screening, any history or evidence of long QT syndrome or QTcF interval >450 msec for males and >470 msec for females (according to Fridericia's correction) at screening
6. Known HIV infection; active hepatitis B or C without concurrent treatment (positive tests for hepatitis B [both HBsAg and HBeAg], or high titer of hepatitis C ribonucleic acid [RNA] >800,000 IU/ml)
7. Uncontrolled and unstable concurrent medical condition including G6PD, psychiatric disorders and alcohol/substance dependence/abuse that will jeopardize the safety of the patient, interfere with the objectives of the study, or affect the patient compliance with study requirements, as determined by the Investigator
8. Patients with concomitant use of medications that alter the absorption or excretion of hydroxychloroquine
9. Patients were considered to be unable to complete the study, or not suitable for the study judged by Investigators
10. Pregnant or breast-feeding women

## 2.2 SCREENING EVALUATION

Patient who had fever (central temperature  $\geq 38^{\circ}\text{C}$ ) or acute upper respiratory symptoms and are tested positive for COVID-19 from respiratory specimen by rRT-PCR methods. According to "the Interim Guideline for the Clinical Management of New Coronavirus (SARS-CoV-2) Infection", the throat swabs, sputum (lower respiratory tract fluid) and serum should be collected while the initial test for confirmation of infection suspected candidate. The same type of respiratory specimens should be collected and assessed for eligibility confirmation in screening evaluation of the study. In addition, Hemogram, biochemistry, urinalysis, chest X ray and ECG will be checked. Above baseline evaluation could be done before signing the written informed consent form as clinically needed.

## **2.3 RANDOMIZATION (OR STRATIFICATION) PROCEDURES (APPLICABLE FOR RANDOMIZED CONTROLLED TRIALS)**

After signing the written informed consent form, 3-digits screening number contains the first letter of S (starting from S01) will be assigned to subject sequentially. Subject screened but not eligible will have the screening number only.

Subjects who meet all study criteria after the screening evaluation will be randomly assigned to in a 2:1 ratio, stratified with mild illness (no pneumonia) and moderate disease (with pneumonia), to receive hydroxychloroquine or have standard of care (SOC) treatment. A randomization number (starting from 001) will be sequentially assigned to an eligible subject. Replacement subjects will be assigned the corresponding number, starting from 101 (i.e., the replacement subject for 005 will be assigned a number of 105, etc.).

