## **3 STUDY IMPLEMENTATION**

### **3.1 STUDY DESIGN**

This is a multi-center, randomized, open-label, controlled trial to evaluate the efficacy and tolerability of Hydroxychloroquine Sulfate (HCQ) in adult Patients with mild to moderate coronavirus disease (COVID-19) compared to standard of care treatment (SOC). The primary endpoint for the study is to evaluate the efficacy of HCQ, with respect to the time to negatively rRT-PCR assessments from the randomization date up to 14 days. The secondary endpoint is to evaluate the efficacy of HCQ in the aspect of virological assessments and the change of clinical symptoms. In addition, the safety and tolerability of HCQ will be evaluated during treatment period in COVID-19 patients.

The study will employ an open-label parallel design, to evaluate the efficacy and safety between hydroxychloroquine sulfate (plaquenil) and controlled standard of care treatment. The administration plan of HCQ is 400 mg bid on Day 1 and 200 mg bid for 6 days on Day 2-7. All of the enrolled subjects will receive standard of care. The comparison group will receive standard of care, i.e., supportive treatment for subjects with mild COVID-19 clinical illness, and antimicrobial therapy for subjects who developed moderate COVID-19 clinical illness (ceftriaxone 2gm daily for 7 days ± azithromycin 500mg on Day1 and 250mg on Day2-5; or levofloxacin 750 mg daily for 5 days, or levofloxacin 500mg daily or moxifloxacin 400mg daily for 7-14 days for the subjects who had allergic history to ceftriaxone or azithromycin, or per physician's discernation). Oseltamivir 75 mg bid for 5 days will be given for subjects who have concomitant influenza A or B infection. The subjects will be randomly assigned to a 2:1 ratio to receive HCQ + SOC, or SOC alone. The estimated case number will be 30:15. No dose reduction, modification, or change in the frequency of HCQ will be recommended during the study period.

The investigators may determine to switch to HCQ treatment arm on Day 8 if the subjects developed progression of pneumonia clinically, or roentegenographically, or had persistent high viral load without 10 log of decline, compared to baseline data.

An independent data monitoring committee (IDMC) will be instituted to ensure external objective

medical and/or statistical review of efficacy to protect the ethical interests and well-being of participants and to protect the scientific validity of the study.

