### **3.5 CRITERIA FOR REMOVAL FROM PROTOCOL THERAPY AND OFF STUDY CRITERIA**

#### **3.5.1 Off-Study Criteria**

Participants who developed adverse events including grade 3/4 liver toxicity, grade 3 allergic reaction, or other severe adverse events (including progression to the stage of severe pneumonia)

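### Section 2.3 replaces randomised subjects under a number tied to the one replaced; if the arm goes with the number, the replacement's arm can be known before enrolment

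*Protocol*

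**What the plan says.** Protocol section 2.3 sets up two number series. On screening it says "Subject screened but not eligible will have the screening number only". On allocation it says "A randomization number (starting from 001) will be sequentially assigned to an eligible subject", with subjects "randomly assigned to in a 2:1 ratio, stratified with mild illness (no pneumonia) and moderate disease (with pneumonia"). It then adds a third rule: "Replacement subjects will be assigned the corresponding number, starting from 101 (i.e., the replacement subject for 005 will be assigned a number of 105").

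Section 3.1 describes the setting: "This is a multi-center, randomized, open-label, controlled trial to evaluate the efficacy and tolerability". It gives the planned size as "The estimated case number will be 30:15".

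Section 3.5.1 lists off-study events, beginning "Participants who developed adverse events including grade 3/4 liver toxicity, grade 3 allergic reaction, or other severe adverse events", and does not mention replacement. The text at hand passes from section 3.1 to section 3.5, so a trigger for replacement may be stated in a part that is not available here.

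**The concern.** In an open-label trial, concealing the next assignment until the subject is enrolled is the main protection against selective enrolment. Blinding after allocation is a separate matter, and its absence is no reason to give up concealment before allocation.

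A replacement number matched to a particular earlier subject suggests that the slot, arm included, is being refilled. If so, a site that treated the earlier subject knows what the next patient placed in that slot will receive. It also has room to act on this, because exclusion criteria 7 and 9 in section 2.1.2 rest partly on the investigator's judgement of suitability. Who fills the slot can then depend on the arm. Analysing everyone as assigned does not undo selection that took place before assignment.

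**Working it through.** **Is 005 already randomised?** Yes. Screen failures hold only an S-number, and numbers from 001 go only to eligible subjects. Replacing 005 is therefore replacement after randomisation, not the refilling of a failed screening.

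**Is 105 on the sequential list?** No. It lies in a separate series from 101 upwards and equals the replaced number plus 100.

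**Does 105 take the arm of 005?** The protocol does not say. If replacements were drawn afresh, the next sequential number would do; a matched number makes most sense if the slot itself is refilled. Inheritance is thus an inference, and everything below depends on it.

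**Planned size.** 45 × 2/3 = 30 and 45 × 1/3 = 15, which reproduces the stated 30:15.

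**Predictability of one slot.**
- Always guessing HCQ under 2:1: 2/3 = 67% correct.
- Inherited arm, predecessor's arm known: 100% correct.

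**Number of slots.** The protocol gives none, so a range is assumed.
- 10% of 45: 4.5 replacements, or 4.5/49.5 = 9.1% of all enrolled.
- 20% of 45: 9 replacements, or 9/54 = 16.7% of all enrolled.

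If the guess is HCQ for each of the 45 original slots and the known arm for each replacement, the share of correct guesses over the whole trial is (30 + r)/(45 + r). For r = 2, 5 and 9 this is 0.681, 0.700 and 0.722, against 0.667 with no foreknowledge.

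**Illustration of bias.** All rates here are assumptions: Day-14 clearance of 70% in both arms, selected replacements clearing at 85%, and everyone analysed as assigned. Replacement is set at 10% or 20% of an arm, so 3 or 6 of 30 on HCQ and 1.5 or 3 of 15 on SOC (expected numbers, hence the fraction).

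| Arm | Replacement 10% | Replacement 20% |
|---|---|---|
| HCQ | (21 + 3 × 0.85)/33 = 71.4% | (21 + 6 × 0.85)/36 = 72.5% |
| SOC | (10.5 + 1.5 × 0.85)/16.5 = 71.4% | (10.5 + 3 × 0.85)/18 = 72.5% |

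- Same replacement rate and same selection in both arms: difference 0.
- HCQ arm only: +1.4 or +2.5 points.
- SOC arm only: −1.4 or −2.5 points.

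Standard error of the difference at 30 v 15: √(0.21/30 + 0.21/15) = 0.145, or 14.5 points. The shifts are 0.01364/0.1449 = 0.09 and 0.025/0.1449 = 0.17 of one standard error.

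**The case against.** The strongest reply is that section 2.3 nowhere says the arm is inherited. Its general sentence has every eligible subject randomised 2:1, a replacement is also an eligible subject, and 105 could be no more than a label. If 105 is freshly randomised, the predictability disappears. That is right as far as it goes, and it is why the point is conditional. But nothing in the available text says that subjects numbered from 101 are newly randomised, and a rule that can be carried out in two ways, one of which breaks concealment, needs correcting in either case.

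Second, bias needs a chain of conditions: inheritance, actual replacements, a site that knows the predecessor's arm, use of that knowledge, and a difference between arms. This stands, and it limits the claim. In a multi-center trial, a site that does not know the arm of 005 gains nothing.

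Third, the illustrated effect is small and uses a Day-14 proportion, whereas the primary endpoint is time to negative rRT-PCR. This also stands. A harsher case does not change the picture: with the same assumed rates, 9 replacements all on HCQ give (21 + 9 × 0.85)/39 = 73.5%, or +3.5 points (0.24 of a standard error). All 9 on SOC give (10.5 + 9 × 0.85)/24 = 75.6%, or −5.6 points (0.39), but that means replacing 9 of 15 subjects.

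Fourth, the main list may itself be more predictable than 67%. With an assumed block of 3 and all earlier arms known, the average best guess is (2/3 + 2/3 + 1)/3 = 78%. The block size is not stated. The 67% is the success rate of always guessing HCQ, not of the best possible guess, so the extra loss from the replacement rule could be smaller than 100% against 67% suggests. An inherited arm would still be fully known.

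**Conclusion.** The concern holds. Section 2.3 replaces subjects who have already been randomised, under a number tied to the subject replaced and outside the sequential list. If the arm goes with the number, as the matching implies but the text does not state, each replacement slot is fully predictable to a site that knows the predecessor's arm. The main list from 001 is untouched.

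The size of any bias cannot be derived from the protocol. Under the assumptions shown it is zero when replacement and selection are alike in both arms. It is 1.4 to 2.5 points when 10-20% of one arm is replaced and the other arm has no replacements, well inside the sampling error. This is a flaw that should be corrected because it weakens the allocation safeguard for no benefit, not because it is likely to overturn the result. Confidence is medium, because inheritance of the arm is inferred.

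**What to change.** Delete the matched-number rule in section 2.3. State instead that any additional subject takes the next concealed number on the stratified 2:1 list for their own severity stratum, in addition to and not in place of the subject who left, who remains in the arm assigned. This removes the foreknowledge created by the matched number and the doubt over whether 105 takes the arm of 005. It also leaves the replaced subject in the randomised comparison.

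A smaller edit, if the numbering must be kept, is to state that subjects numbered from 101 are newly randomised. That closes the concealment gap but does not settle whether 105 stands in for 005 or is added to the trial.

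The cost is one sentence. Final totals may differ slightly from 30:15, which the protocol itself calls an estimate.

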## **2.4 BASELINE EVALUATION**

The day 0 (baseline) assessment of participants will be evaluated as follows: Chest X ray, throat swabs and sputum collection for COVID-19. Hemogram, biochemistry, urinalysis, and ECG, and been considered as baseline. Every effort will be made to collect all types of specimen (throat swabs, sputum, lower respiratory tract fluid, or serum) for rRT-PCR assessment from screening patients in Day 0. For evaluation of primary efficacy endpoint, the type of respiratory tract specimens in each assessment day should be the same with baseline in Day 0.

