#### **6.2 CRITERIA OF PRIMARY ENDPOINTS**

##### **6.2.1 Primary efficacy endpoints**

- Transition time of SARS-CoV-2 nucleic acid rRT-PCR from positive results to negative results in respiratory tract specimen on day 0, 2, 4, 6, 8, 10, 12, 14. For evaluation of primary efficacy endpoint, the type of respiratory tract specimens in each assessment day should be the same with Day 0.

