### **6.3 SECONDARY ENDPOINTS**

#### **6.3.1 Evaluation of Efficacy**

- Virological clearance rate at day 8
- AUC of viral load on day 0, 2, 4, 6, 8, 10, 12, 14

For the above 2 secondary efficacy evaluations, the type of respiratory tract specimens in each assessment day should be the same with Day 0.

- Time to Clinical recovery (TTCR):

TTCR is defined as the time (in hours) from randomization (active or placebo) until normalization of fever, respiratory rate, and oxygen saturation, and alleviation of cough, sustained for at least 72 hours.

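### Does the same-specimen rule leave the primary endpoint undefined when throat swab and sputum are both taken on Day 0?

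*Protocol*

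**What the plan says.** Section 2.4 schedules "throat swabs and sputum collection for COVID-19" on Day 0 and asks sites to try to obtain every specimen type, lower respiratory tract fluid included. It then adds, for the primary endpoint, that "the type of respiratory tract specimens in each assessment day should be the same with baseline in Day 0".

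Section 6.2.1 defines the primary endpoint as the time of transition "from positive results to negative results in respiratory tract specimen on day 0, 2, 4, 6, 8, 10, 12, 14" and repeats the matching rule. Section 6.3.1 extends it to Day-8 clearance and viral-load AUC: "For the above 2 secondary efficacy evaluations, the type of respiratory tract specimens in each assessment day should be the same with Day 0".

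Two earlier sections also bear on specimen type. Inclusion criterion 2 (section 2.1.1) requires a confirmed infection "with available same type of upper respiratory tract specimens from screening evaluation" to the initial test. Section 2.2 lists throat swab, sputum and serum for the initial test and says that "The same type of respiratory specimens should be collected and assessed for eligibility confirmation in screening evaluation of the study".

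On size, section 3.1 states: "The estimated case number will be 30:15".

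**The concern.** The matching rule is written for the primary endpoint, so one expects it to yield one value per patient. It does not always do so. With two respiratory types taken on Day 0, the throat series and the sputum series each match Day 0. If both are positive at baseline and they turn negative at different visits, four derivations fit the text: throat only, sputum only, first negative on either, or negative on both. Day-8 clearance inherits the same choice. AUC needs a decision on which series, or which summary of the two, is integrated.

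The trial is open-label. If the derivation were settled late, by someone who knew the results and the arms, it could be chosen to favour one arm. With so few patients, a handful of such choices would matter.

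**Working it through.** **Which patients are affected.** Three conditions must hold together: two respiratory types were obtained, both were positive on Day 0, and they cleared at different visits. Section 2.1.1 describes mild illness as cough that may or may not produce sputum, and section 2.4 promises only an effort to collect all types, so some patients will have one type only. For a patient who is throat-negative and sputum-positive on Day 0, only sputum can make a positive-to-negative transition. The open question there is whether that patient counts, not which time applies. The protocol gives no frequency for any of these groups.

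**How far apart the two times can be.** Post-baseline visits are Days 2, 4, 6, 8, 10, 12 and 14, seven in all. A patient who clears both types by Day 14 has 7 × 7 = 49 possible pairs of first-negative visits. In 7 they coincide and in 49 − 7 = 42 they differ. The smallest gap is 2 days and the largest is 14 − 2 = 12 days. These are counts of cells, not probabilities.

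**Step size at Day 8.** One discordant patient changes the clearance rate by 1/30 = 3.3 points in the HCQ arm, or 1/15 = 6.7 points in the control arm.

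**Effect on a rate and on the contrast.** Assume, for illustration only, that all patients are positive on both types on Day 0, that each type has cleared in p = 0.5 of patients by Day 8, and that the between-type correlation is φ. Then P(both negative) = p² + φp(1 − p), and P(either negative) = 2p − P(both negative).

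| φ | Both negative | Either negative | Gap |
|---|---|---|---|
| 0.9 | 47.5% | 52.5% | 5 points |
| 0.7 | 42.5% | 57.5% | 15 points |
| 0.5 | 37.5% | 62.5% | 25 points |

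These are rates within one arm. If the arms share p and φ (no treatment effect), a single rule gives the same rate in each. At φ = 0.5 the difference is 62.5 − 62.5 = 0 under one rule and 37.5 − 37.5 = 0 under the other. The same holds for transition time: if the pair of clearance times has the same distribution in both arms, so does any fixed function of the pair. A uniform rule therefore creates no false difference. The 5 to 25 points become a spurious effect only if one arm is read by one rule and the other arm by the other.

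**Effect on level and event count.** A simulation on assumed inputs (lognormal clearance, log-SD 0.5, throat median 6 to 8 days, sputum median 6 to 12 days, correlation 0.3 to 0.7) gave different transition visits in about 65% to 85% of patients. Expected events by Day 14 among 45 patients were about 40 to 45 for either negative and 25 to 42 for both negative. So the choice can alter the median and the precision. None of these inputs comes from the protocol, and the simulation has no treatment arms.

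**The case for a change.** The strongest case for a change is that the protocol did not leave this subject to the analysis plan. It set a specimen rule for its own primary endpoint, and the rule does not give a unique value. Reading it as a collection rule (repeat whatever was taken on Day 0) secures matched samples but still leaves two results per visit. The specimen measured is part of what the endpoint is, and one sentence would settle it.

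Much of that stands. No section designates the endpoint specimen, and inclusion criterion 2 governs eligibility, so it does not formally fix the throat swab for the endpoint. It does give the upper specimen some textual support, because section 2.3 randomises only patients who meet all criteria and this is the one specimen class those criteria mention. The four readings are therefore not equally backed.

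What does not stand is the step from incomplete to wrong. The rule does a useful job: it stops a positive sputum on Day 0 from being counted as cleared by a negative throat swab later. It conflicts with no other section. How two parallel series become one event time is derivation detail. Only the protocol is at hand, and a statistical analysis plan commonly supplies that detail. The open-label worry needs a choice made patient by patient or arm by arm after results are seen, and no section allows that. Nor is there one obvious wording to insert: the upper specimen and clearance of all types are both defensible. Fuller rules that move some patients to another specimen, or drop randomised patients who are negative on Day 0, would bring problems of their own.

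**Conclusion.** No change to the protocol follows. The protocol leaves one derivation step open, and analysts can fill it sensibly by fixing a single specimen type, or a single combination rule, for all patients before results are examined, with the other type as supportive. Applied alike in both arms, any of the candidate rules gives a valid comparison. They differ in what clearance means, in its level and in precision.

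The size is bounded for one patient (2 to 12 days in transition time; 3.3 or 6.7 points in an arm's Day-8 rate) and unknown for the trial, because the documents do not say how many patients are positive on both types or how often the types clear apart. The larger figures rest on assumed clearance rates, correlations and medians, and show no bias in the between-arm contrast. The conclusion rests on one condition: a single rule, set without reference to results by arm. Evidence that the series had been chosen after unblinded review would change it.
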